#### Notes:

A Informed Consent Form (ICF) signed and dated, before any trial procedure is performed. In order to provide the Investigator with an adequate time frame to organize and perform the clinical tests and assess the inclusion/exclusion criteria on the Subject, the screening phase was set up a maximum duration of 30 days (V0). During this screening phase the size of tumor should be verified. If the volume of tumor resulted lower than 5mm after the prone breast MRI performed in the screening phase, the withdrawal of the patient will be considered as a screening failure. After the ICF is signed, a supine MRI will be scheduled as soon as possible but according to local standard procedure.

Data collected by supine MRI (performed at V1):

- tumor maximum diameter (cm), tumor volume and ideal specimen volume (mm^3).

Data collected by prone MRI (performed at V0):

- presence of satellite lesion(s) (Y/N) and maximal tumor diameter (mm).

|  |                           |                  |                |
|--|---------------------------|------------------|----------------|
|  | Form               | Form Nr.  | 1M-DMST-011-A3 |
|  | Statistical Analysis Plan | Page      | 10 of 116      |
|  |                           | Version # | 0.1            |

B Medical history includes patient-reported bra cup size and documentation of any contraindications to MRI (e.g., implanted electrical devices exist), history of adverse reactions to gadolinium, breastfeeding or pregnancy.

C Physical examination includes weight, height, distance from sternal notch to the nipple, the circumference around the breast and arms, calculation of BMI, and specific documentation that the breast cancer cannot be palpated.

D Laboratory Tests include:

- serum creatinine levels to calculate the glomerular filtration rate (GFR), acid uric for renal dysfunction;
- complete blood count;
- electrolytes (sodium, potassium, chloride, bicarbonate).

E For females of childbearing potential only, urine pregnancy test will be performed with dipsticks supplied by the Investigator. Results must be available before any procedure.

F All Subjects will have had a mammogram and prone MRI assessment prior to enrollment. If breast ultrasound images are obtained, they will be available to the study team. The results from pathologic analysis of diagnostic core biopsy specimens, including IBC vs. DCIS, will be documented. Results of imaging studies should be obtained within 3 months of study enrollment.

G After the tumor specimen is removed:

- the specimen volume will be determined by water displacement,
- a specimen mammogram will be obtained and then the specimen will be sent to the pathologist for evaluation of the positive margins.
- the presence of invasive cancer in core biopsy (Y/N), presence of DCIS in core biopsy (Y/N), presence of invasive cancer in lumpectomy specimen (Y/N), presence of DCIS in lumpectomy specimen (Y/N), subtype of invasive cancer (ductal vs lobular vs other), Maximal tumor diameter on pathology report of lumpectomy specimen (mm), shave biopsy done during surgery (Y/N, and if done how many) will be recorded.

H Surgery will be scheduled 10-40 days after the supine MRI. Subjects will have a pre-surgical contrast-enhanced supine MRI. MRI images will be transmitted to CairnSurgical where a study radiologist will outline the tumor edges on the supine MRI. These supine MRI images will be used to fabricate a BCL using 3D printing. The Investigator will perform the BCS using the BCL device. Specimen volumes will be determined by water displacement. Specimen mammograms will be obtained. Additional shave biopsies may be taken after the initial tumor resection at the discretion of the investigator. The specimen will be sent to Pathology.

I If, for any reason, the PI is not able to fill the 5-point Likert Scale soon after surgery, the procedure must be completed prior discharge of the patient.

|  |                           |                  |                |
|--|---------------------------|------------------|----------------|
|  | Form               | Form Nr.  | 1M-DMST-011-A3 |
|  | Statistical Analysis Plan | Page      | 11 of 116      |
|  |                           | Version # | 0.1            |

### 1.3. Study Objective(s)

#### 1.3.1. Primary Objective(s)

The primary objective is to evaluate the performance of the BCL in reducing the positive margin rate when the BCL system is used to guide a surgeon performing partial mastectomy.

#### 1.3.2. Secondary Objective(s)

The secondary objectives of the study are:

- To calculate the specimen volume after BCL guided partial mastectomy;
- To evaluate the surgeon's perception of ease of use of the BCL system;
- To evaluate the safety and tolerability of BCL;
- To evaluate the patient's satisfaction;
- To compare the ideal specimen volume to the actual specimen volume and tumor volume;
- To record important clinical data on the removed specimens.

#### 1.3.3. Other Objective(s)

Not applicable for this study.

## 2. Study documents

The following documents were used in the writing of the present SAP:

- Study protocols:
  - "CairnS\_BCL\_CIP\_V2.0\_Amend1\_ITA-SWISS\_21November2023.pdf";
  - "CS-BCL-EU2021\_CIP\_V2.0\_SubAmend 2\_GERMANY\_21Nov2023.pdf"
- pCRF:
  - "CS-BCL-EU2021\_pCRF\_V2.0\_3.12.2023.pdf";
- Likert ease of use for BCL:
  - "CS-BCL-EU2021\_Likert ease of use BCL\_V1\_ENG\_05Oct2021.pdf"
  - "CS-BCL-EU2021\_Likert facilita uso BCL\_V1\_ITA\_05Oct2021.pdf"
- Likert ease of use for Visualizer
  - "CS-BCL-EU2021\_Likert ease of use Visualizer\_V1\_ENG\_05Oct2021.pdf"
  - "CS-BCL-EU2021\_Likert facilità uso Visualizer\_V1\_ITA\_05Oct2021.pdf"
- BREAST-Q:
  - "BREAST-Q BCT V2.0 English - Sat. w Breasts.pdf"
  - "BREAST-Q BCT V2.0 Italian IT (L) - Sat. w Breasts.pdf"
  - "BREAST-Q BCT V2.0 German DE (L) Sat. w Breasts.pdf"

|  |                           |                  |                |
|--|---------------------------|------------------|----------------|
|  | Form               | Form Nr.  | 1M-DMST-011-A3 |
|  | Statistical Analysis Plan | Page      | 12 of 116      |
|  |                           | Version # | 0.1            |

### 3. Database coding

AEs will be coded using MedDRA® dictionary version 27.0 (Lowest Level Term (LLT), Preferred Term (PT), and System Organ Class (SOC)).

To describe prior and/or concomitant medications, medications will be coded with active ingredients reported in English.

|  |                           |                  |                |
|--|---------------------------|------------------|----------------|
|  | Form               | Form Nr.  | 1M-DMST-011-A3 |
|  | Statistical Analysis Plan | Page      | 13 of 116      |
|  |                           | Version # | 0.1            |

## 4. Analysis Sets and Subgroups

### 4.1. Analysis sets

The data sets defined for the study in accordance with the study protocol are outlined in the following table.

|                            |   |
|----------------------------|---|
| Safety Analysis Set (SAS): | The "Safety Set" will include All patients undergoing surgery with the BCL System.  |
| Full Analysis Set (FAS):   | The "Full Analysis Set" will include All patients undergoing surgery with the BCL System.   |
| Per-Protocol Set (PPS):    | The "Per-Protocol Set (PPS)" will include all the FAS patients who (a) met all inclusion/exclusion criteria liable to affect the performance assessment, (b) did not present serious deviations of the protocol that may affect efficacy. |

Definition of major protocol deviations and selection of subjects accordingly will be performed prior to Database Lock (DBL).

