### 1.2.2 General Description

The BCL System is a patient-matched Breast Conserving Surgery (BCS) guidance device derived from *supine* breast magnetic resonance imaging (MRI) data. The device allows the surgeon to transfer surgical cues associated with a patient's breast and breast cancer to help guide the surgeon with the tumor resection procedure.

The BCL is created using an additive manufacturing (3D printing) process involving a digital model that is derived from the Subject's *supine* MRI data.

The BCL model is constructed from a biocompatible, semi translucent, UV-cured, photopolymer resin material using the stereolithography (SLA) additive manufacturing process.

The BCL System is comprised of the following components and accessories:

- BCL Kit, including:
  - Sterile patient-specific BCL model
  - BARD® GHIATAS® Beaded Breast Localization Wires (up to 6, patient-specific sizes; sizes are limited to 5 cm, 7 cm, 9 cm, or 14 cm)
  - Medical grade permanent marking pen and ruler (Viscot Medical, LLC Sterile Reg/Fine Tip XL Prep Resistant Ink Marker)
- MR Kit, including:
  - Viscot Medical, LLC Sterile Reg/Fine Tip XL Prep Resistant Ink Marker (x1)
  - 3M™ Tegaderm™ Transparent Dressing (x3)
  - Izi Medical Products MRI fiducial markers (x5)
- MR Coil Pad Kit, including:
  - MRI Coil Cushion (pad) (x2)

	Study Title		An Interventional, Post-Market Study to Evaluate the Performance of a Custom-made Medical Device, "Breast Cancer Locator Guidance (BCL)" System, in Breast-conserving Surgery (BCS)	
	Study ID	CS-BCL-EU2021	Sponsor	CairnSurgical Inc.
	Date	25Nov2022	Version	1.0 Substantial Amendment 1_GERMANY

The BCL device itself doesn't contain any software. However, various software tools are used to design the BCL:

- Combination of commercial off the shelf (COTS) software and proprietary CairnSurgical software components to create digital anatomical models of the Subject's breast surface, tumor, chest wall, the BCL device model, and patient-specific reports of geometrical data to relevant to BCS.
- An optional web browser-based interactive surgical plan Visualizer will be provided. The Visualizer software displays the 3D model of the BCL, the tumor, and chest wall, with visual markers to show locations where the tumor is closest to the skin and closest to the underlying chest wall/muscle (including distances from tumor to skin and the tumor to the chest wall).

[figure not shown]

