### 2.3.2 Secondary Endpoints

- To calculate the specimen volume after BCL guided partial mastectomy, the water displacement method (WDM) will be used (results will be obtained within the same day of surgery).
- To evaluate the surgeon's perception of ease of use of the BCL System, a 5 Likert scale will be used at V2;
- To evaluate the safety and tolerability of BCL through physical examination and AEs assessment including the relationship of the AE to the BCL System at V1, V2, V3, V4;
- To evaluate the patient's satisfaction, the BREAST-Q will be used at EOS/V4.

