### 2.5.4 Definition Of Datasets

For the statistical analysis the enrolled Subjects will be divided into the following datasets:

	Study Title	An Interventional, Post-Market Study to Evaluate the Performance of a Custom-made Medical Device, "Breast Cancer Locator Guidance (BCL)" System, in Breast-conserving Surgery (BCS)		
	Study ID	CS-BCL-EU2021	Sponsor	CairnSurgical Inc.
	Date	25Nov2022	Version	1.0 Substantial Amendment 1_GERMANY

Safety Analysis Set (SAS):	The "Safety Set" included all enrolled patients undergoing surgery with the BCL System.
Full Analysis Set (FAS):	The "Full Analysis Set" (FAS): this set included all enrolled patients undergoing surgery with the BCL System.
Per-Protocol Set (PPS):	The "Per-Protocol Set (PPS)" would include all the FAS patients who (a) met all inclusion/exclusion criteria liable to affect the performance assessment, (b) did not present serious deviations of the protocol that may affect efficacy.

Definition of major protocol deviations and selection of Subjects accordantly will be performed prior to database lock.

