Subjects will undergo a contrast-enhanced supine MRI at their local facility using a body coil, applied on top of a specially designed foam support structure, with MRI sequences that are designed to obtain both breast surface contour and breast tumour signatures, as detailed in the [MRI Kit](#) and [MRI Acquisition Procedure Manual](#). The Subject's arm on the cancer side will be parallel to the body. Two marks will be placed on the breast using the marker provided with the investigational device for this purpose at exactly 4 cm directly medial and 4 cm directly cranial to the nipple. An MRI fiducial will be placed over each mark for the duration of the MRI. A fiducial will also be placed on the nipple, but no mark will be placed on the nipple. After the MRI is completed, the fiducials will be removed, marks will be reinforced by the MRI technician, and a transparent plastic dressing (Tegaderm™) will be placed over each mark. Patients with a documented Tegaderm™ allergy will be excluded from the study. For patients who develop a possible allergic reaction to the Tegaderm™, if the reaction is mild (e.g., mild redness with no or mild symptoms) the Tegaderm™ should be left in place. If the reaction is moderate to severe and symptomatic (e.g., very itchy or painful) the Tegaderm™ should be removed, the mark should be reinforced, and an alternative hypoallergenic plastic dressing should be placed. The Subject will be instructed that it is important to leave the Tegaderm™ dressings in place over the marks until surgery. If a Tegaderm™ dressing is removed for any reason, the Subject will be instructed to call her Investigator and have the Investigator remark and cover the site as soon as possible.

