#### Risks associated with the MRI

1. Anaphylactic allergic reaction from Gadolinium based intravenous contrast.  
*Likelihood:* 0.001-0.01% [28].  
*Clinical consequences:* hypotension.
2. Gadolinium based contrast adverse reactions (injection site pain, headache, nausea, paresthesia, dizziness).  
*Likelihood:* 0.07%-2.4% [28].  
*Clinical consequences:* most reactions are mild and do not require therapy.
3. Gadolinium based contrast induced nephrogenic systemic fibrosis.  
*Likelihood:* very rare if patients with kidney disease are excluded [28].
4. Gadolinium deposition in organs, including but not limited to brain, bone, skin, kidney, liver, and spleen.  
*Likelihood:* high  
*Clinical consequences:* in autopsy studies no histologic evidence of toxicity in the human brain has been demonstrated. No adverse clinical consequences of gadolinium retention in the brain and other organs have been proven [28], [29].  
While negative effects of gadolinium retention have not been established in patients with normal renal function, certain patients might be at higher risk. These include patients requiring

	Study Title	An Interventional, Post-Market Study to Evaluate the Performance of a Custom-made Medical Device, "Breast Cancer Locator Guidance (BCL)" System, in Breast-conserving Surgery (BCS)		
	Study ID	CS-BCL-EU2021	Sponsor	CairnSurgical Inc.
	Date	25Nov2022	Version	1.0 Substantial Amendment 1_GERMANY

multiple lifetime doses, pregnant and pediatric patients, and patients with inflammatory conditions [30].

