Adverse events (AEs) will be reported on a per-patient basis. This implies that even if a patient reported the same event repeatedly, the event will be counted only once. In the latter case, the event will be assigned the worst severity and strongest relationship to the investigational study medication. The presentation of AEs is therefore restricted to the incidence per patient of AEs assigned to the Treatment Period.

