##### Imputations for missing values:

Not applicable for this study.

|                               |          |                |
|-------------------------------|----------|----------------|
| Analysis Sets to be used for: | Tables   | SAS            |
|                               | Listings | SAS            |
|                               | Figures  | Not applicable |

Patients' data will be summarized as follows:

|                                      |   |
|--------------------------------------|---|
| Table 20. Device deficiencies | Counts and percentages of Device Deficiencies will be provided for all Patients included in SAS by study visit. |
|--------------------------------------|---|

Patients' data will be listed as follows:

|  |  |
|--|--|
| Listing 29. Device deficiencies | Listing of all Device Deficiencies by study visits for SAS patients. |
|--|--|

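### The Safety Set begins at BCL surgery, so adverse events and device deficiencies in patients scanned at V1 but not operated on with the BCL are missing from every AE and deficiency table

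*SAP*

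**What the plan says.** SAP 4.1 states that the Safety Set "will include All patients undergoing surgery with the BCL System". Protocol 2.5.4 has the same rule: its Safety Set "included all enrolled patients undergoing surgery with the BCL System". In both documents the Full Analysis Set is defined in the same way, so the two sets coincide.

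The safety endpoint in protocol 2.3.2 covers "AEs assessment including the relationship of the AE to the BCL System at V1, V2, V3, V4". Protocol 2.10.1 has AEs assessed from V0 to the end-of-study visit and device deficiencies recorded at V1 and V2.

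SAP 6.4.1 and 6.4.5 place the AE and deficiency tables on the Safety Set. For deficiencies the wording is "Counts and percentages of Device Deficiencies will be provided for all Patients included in SAS by study visit". SAP 6.4.1 adds that the presentation of AEs is "restricted to the incidence per patient of AEs assigned to the Treatment Period", a period the SAP does not define. SAP 5.2 puts all listings on the set of all patients, while 6.4.1 and 6.4.5 put theirs on the Safety Set.

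SAP 1.2.3 foresees withdrawals before BCL surgery, treats them as drop-outs, and gives no rate.

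**The concern.** A safety population should start where exposure starts. Here exposure to study procedures and to parts of the device comes 10 to 40 days before entry to the Safety Set. A patient who leaves after a reaction at V1, or whose BCL cannot be made or used, is removed from the table by the event the table is meant to count. Where the event is the reason for not operating, the omission favours the device.

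Protocol 1.4 gives confirming the device's safety and performance as an aim of the study. With about 35 patients, a single event decides whether a row reads zero. The Treatment Period wording creates a related gap: without a definition, V1 events could also be left out for patients who were operated on.

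**Working it through.** **Where exposure, collection and analysis each begin**

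1. Device. Protocol 1.2.2 states "The BCL System is comprised of the following components and accessories", and the list includes the MR Kit (marker, dressings, fiducials) and the MR Coil Pad Kit. Both are used at V1.
2. Procedure. Protocol 2.10.2: "Subjects will undergo a contrast-enhanced supine MRI at their local facility using a body coil". This is the V1 visit.
3. Recognised risk. Protocol 2.11.3 lists "Anaphylactic allergic reaction from Gadolinium based intravenous contrast" and puts other contrast reactions at 0.07% to 2.4%. Protocol 2.10.2 describes possible reactions to the dressing.
4. Collection. AEs are collected from V0 and deficiencies at V1 and V2.
5. Analysis. The AE and deficiency tables require BCL surgery at V2.

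Steps 1 to 4 begin at or before V1 and step 5 begins at V2. Enrolled patients scanned at V1 and not operated on with the BCL fall between them.

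**What other outputs would show**

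Table 1 (reasons for exclusion from each set), Table 2 and Figure 2 (withdrawal reasons), Table 3 (attendance by visit) and Listing 1A all use all patients. They would show that a patient left and a coded or free-text reason. None gives the event term, severity or causality.

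**Size**

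The plan has no figure for this point. Its nearest figure is N=35 with an interval width of 15% for the positive margin rate. Clopper-Pearson with n = 35 and x = 0.03 × 35 = 1.05 gives 0.09% to 15.14%, a width of 15.05%, so the width reproduces. In SAP 1.2.3 that N counts operated patients with a margin assessment, so the Safety Set does not affect it.

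The documents give no drop-out rate d between MRI and surgery, so d is assumed. With 35 operated, the number scanned is 35/(1 − d), rounded to the nearest patient:

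| d (assumed) | Scanned | Omitted | One omitted event: planned table | One omitted event: all scanned |
|---|---|---|---|---|
| 0% | 35 | 0 | – | – |
| 5% | 35/0.95 = 36.8, so 37 | 2 | 0/35 | 1/37 = 2.7% |
| 10% | 35/0.90 = 38.9, so 39 | 4 | 0/35 | 1/39 = 2.6% |
| 15% | 35/0.85 = 41.2, so 41 | 6 | 0/35 | 1/41 = 2.4% |

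The last two columns assume that an event occurs. For contrast reactions alone, the chance of at least one among k omitted patients is 1 − (1 − r)^k. With k = 2 and r = 0.0007 this is 0.1%. With k = 6 and r = 0.024 it is 1 − 0.976^6 = 13.6%. This treats omission as unrelated to the reaction. If reactions cause omission, their rate among omitted patients would be higher.

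**The case against.** The strongest reply is that little may be lost. Safety is handled descriptively, with no test or threshold. The drop-out rate is unknown and could be zero. Protocol 2.11.3 describes most contrast reactions as mild, so many affected patients would still be operated on and counted. Protocol 2.11.5 excludes patients who reacted to gadolinium at their earlier prone MRI. All of this stands, and it limits the expected size. It does not bring back the events of a patient who leaves before surgery.

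Four stronger readings are tempting, and the documents do not support them:

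- That the SAP has no wider population. It uses all patients for disposition, protocol violations and eligibility. What it lacks is a wider set for safety tables.
- That a deficiency serious enough to stop a BCL being used can never be tabulated. Protocol 1.3 supplies one additional BCL, so a patient operated on with the spare stays in the Safety Set. V1 deficiencies in operated patients are also counted. Loss from the listings is uncertain because SAP 5.2 and 6.4 conflict.
- That the events go unrecorded. They are collected, and protocol 3.9 and 3.10 require individual reporting of unanticipated serious device effects and of deficiencies that could have led to a serious one.
- That the high likelihood of gadolinium deposition in protocol 2.11.3 enlarges the problem. No planned assessment measures deposition, and the same section says no adverse clinical consequences have been proven.

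**Conclusion.** The point holds for the AE and deficiency tables. On the plain wording of SAP 4.1 and protocol 2.5.4, events in patients scanned at V1 but not operated on with the BCL are left out, although the endpoint and the data collection include V1. Where the event itself prevented the surgery, the omission favours the device.

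The size is unknown and may be zero. The illustration of 2 to 6 omitted patients per 35 operated, with one event reading 0/35 instead of 2.7% to 2.4%, rests entirely on the assumed 5% to 15% drop-out and on an event occurring. The case for changing the plan is that it contradicts its own endpoint and that some patients are excluded because of the outcome being counted. It does not depend on a large expected loss. The primary analysis and N=35 are unaffected.

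**What to change.** - Define the Safety Set as all enrolled patients in whom any V1 study procedure (supine MRI or use of the MR Kit) was started. Keep the Full Analysis Set at BCL surgery.
- Run the AE and device-deficiency tables on that set, with the BCL-operated subset in a parallel column. Separate events before and after the start of surgery.
- Replace the Treatment Period restriction in SAP 6.4.1 with an explicit window that includes V1. Keep AEs collected from V0 in the listings, so that the new window discards nothing already recorded.
- Set the safety listings in SAP 6.4 and their shells to all patients, in line with SAP 5.2.
- The rule comes from the protocol. SAP 1.1 cites protocol version 2.0, which is later than the one reviewed here, so amend the current version or record the departure in SAP section 7, which now states that there are none. The SAP is at version 0.1, so the change can be made before it is finalised.

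The cost is wording, one extra column and a slightly larger denominator, from data already on the CRF. The larger denominator would dilute surgical AE rates if shown alone, hence the parallel column. Follow-up will be thinner in patients not operated on: protocol 2.9 specifies a final examination only for those who had BCL surgery, although 5.1.1 asks for an exit visit where possible. The tables should say so in a footnote.
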